8.3. Study Procedures

An overview of the study visit and procedures schedule is presented in **Appendix 4** (below) and **Figure 1** (page 12). The text below is additional information on visit-specific study procedures.

8.3.2. Screening and Enrollment Visit

The screening and enrollment visit may be conducted as a split visit as needed. Young women who are eligible and agree to study participation will be consented for 3 months of follow-up. The following procedures will take place:

- 1. Review and obtain written informed consent.
- 2. Confirm/Record locator information and phone number and contact preferences.
- 3. Assign a unique study identification number
- Assess eligibility (e.g., age 18-25 years, newly initiating PrEP at the clinic, symptoms of common mental disorders), including Adult Primary Care Guidelines screening questions and the SRQ-20
 - a. If participants report suicidal ideation or intent, have untreated or severe somatic symptoms or have other active psychiatric symptoms (e.g., hallucinations) the participant will be referred for assessment by a trained health professional (see Section 4.2).

Participants that are already on treatment with stable symptoms may continue to randomization.

- 5. Offer enrolment to eligible participants and refer ineligible for additional services if needed.
- Collect additional data on past mental history, participation in other mental health or HIV interventions, and other psychosocial and behavioral data (see Section 6).
- 7. Randomize participant to either Youth Friendship Bench SA intervention or the standard-of-care condition.
 - a. Participants randomized to the Youth Friendship Bench SA intervention will complete their first counseling session at this visit.
 - i. Collect preferences for SMS appointment reminders (see Section 4.3)
 - ii. Schedule participant for their Week 2 visit in 14 days. They will be offered the option to complete the Week 2 visit in-person or remotely (over the phone).
 - Standard-of-care participants will be scheduled for their next clinic visit at Week 4 in 30 days. They will not receive appointment reminders or remote services.

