	All participants will be offered PrEP in accordance with national PrEP guidelines as part of routine care. We will also provide all participants with brief PrEP adherence counseling based on their urine POC assay results at the Week 4 and Week 12 visits. This adherence counseling will be in addition to their Youth Friendship Bench SA or standard-of-care mental health service delivery	
	All participants will be followed for three months.	
	We will conduct qualitative data collection with a purposive sample of up to 30 AGYW in the trial (between Week 4 and Week 12) and 15 health care providers and key informants to characterize themes around acceptability, appropriateness, and feasibility of Youth Friendship Bench SA and the urine POC TFV assay. We will also conduct ethnographic clinic observations throughout the study period (to 2 times per month).	
Study Population:	HIV-uninfected women ages 18-25 in Johannesburg, South Africa, who have symptoms of common mental disorders as evidenced by a score greater than or equal to 7 on the SRQ-20.	
Study Size:	Up to 110 women who accept PrEP will be consented and randomized	
Outcome measures	We have co-primary outcomes: PrEP adherence and common mental disorder symptoms. The PrEP adherence primary outcome is the proportion with PrEP adherence at Month 3, defined as tenofovir (TFV) concentrations ≥1500 ng/mL in urine measured using a urine POC assay. We will also assess the short-term effect of the Youth Friendship Bench SA intervention on PrEP adherence using the urine POC assay at the Week 4 visit.	
	The mental health related primary outcome is the proportion with reduced symptoms of common mental disorders (SRQ-20 scores <7) at Month 3, measured using the SRQ-20.	
Study Duration:	Approximately 36 months, including submissions to Institutional Review Boards (IRBs) and study start up activities (6 months), recruitment and enrollment (12 months), participant follow up (3 months following the last enrolled participant), and data analysis (remaining time through 36 months).	
Study Site:	Ward 21 public clinic in Johannesburg, South Africa.	

OVERVIEW OF STUDY DESIGN

Figure 1. Study schema for the evaluation of the Youth Friendship Bench SA counseling intervention

AGYW=adolescent girls and young women; SRQ-20=self reporting questionnaire 20-item; SOC=standard of care; IDIs=indepth interviews; POC=point-of-care

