7.2. Study Population

Sexually active young women ages 18-25 who are seeking PrEP at the Ward 21 Department of Health Clinic, in Johannesburg, South Africa, and who have mild-to-moderate symptoms of common mental disorder as defined below.

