7.3. Eligibility

7.3.2. Inclusion Criteria

Young women who meet all of the following criteria are eligible for enrolling in this study:

- Female 18-25 years of age at screening
- Documentation of symptoms of a common mental disorder, as evidenced by a score greater than or equal to 7 on the Self Reporting Questionnaire 20-item (SRQ-20)
- Willingness to enroll and be randomized to either the Youth Friendship Bench SA or standard-of-care mental health services
- Written informed consent (obtained from participant or participant's legal representative and ability for participant to comply with the requirements of the study.
- Able to verbally communicate in one or more study languages to ensure participation in the counseling sessions (English, isiZulu)
- Taking PrEP at the Ward 21 clinic, as determined by clinic records. PrEP provision will be conducted by the clinic following National PrEP Guidelines and will not be part of study-specific procedures.

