7.3.3. Exclusion Criteria

Young women who meet any of the following criteria will be excluded from enrolling in this study:

- Not on PrEP and/or not intending to use PrEP for the duration of the study
- Planning to relocate in the next three months
- Report of suicidal intent or self harm
- Active, unmanaged mental health disorders, including untreated or severe somatic symptoms and active psychiatric symptoms (e.g., hallucinations)
- Reactive or positive HIV test at enrollment (based on clinic records only; we will not perform HIV testing under this protocol)

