8.0 STUDY PROCEDURES AND INTERVENTIONS

8.1. Recruitment and Screening Process

Recruitment and demand-creation activities will frame mental health issues from an empowerment-based lens. All recruitment materials will be approved by IRBs/ECs at the University of the Witwatersrand and the University of California at San Francisco prior to the start of enrollment. Recruitment will take place at the GDOH Ward 21 Adolescent Clinic. We will display posters and pamphlets about our study in the clinic. Potential participants will be identified through referral by clinic personnel (nurses, PrEP adherence counselors, receptionists). Clinic personnel will identify AGYW seeking PrEP either at initiation or follow up

and will approach these AGYW during their clinic visits to offer screening for Youth Friendship Bench SA intervention (which will subsequently be conducted by the Youth Friendship Bench SA lay counselor). All AGYW will be informed that participation in the Youth Friendship Bench SA intervention will not prevent them from receiving standard-of-care mental health treatment or from having their case elevated to a social worker or psychologist as needed, in addition to their possible receipt of the Youth Friendship Bench SA counseling intervention.

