11.3. Accrual, Follow-up, and Sample Size

We will randomize 110 AGYW in a 1:1 ratio to either our adapted intervention or standard-of-care mental health services over a 12-month study period (approximately 9-10 AGYW enrolled per month). Based on current levels of AGYW receiving PrEP at the public health clinic in Johannesburg, and reporting symptoms of common mental disorders and receiving referral services, we will likely need to screen approximately 18-20 AGYW per month to meet our enrollment targets. Based on prior PrEP studies with AGYW in this setting (HPTN 082, PrEP SMART, POWER), we expect to retain 85-90% of AGYW through three months of follow-up.

For our primary outcome of PrEP adherence, if we assume 40% PrEP adherence in the standard-ofcare arm (as was seen in the HPTN 082 trial with AGYW in this setting) and an alpha of 0.05, we will have 80% power to detect at least a 20% difference in the proportion with adherence between arms.

For our primary outcome of common mental disorder symptoms, if we assume 50% prevalence of symptoms of common mental disorders (again, as was seen in the HPTN 082 and PrEP SMART trials) and an alpha of 0.05, we will have 80% power to detect at least a 25% difference in the proportion with symptoms of common mental disorders between arms.

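### The enrollment-visit eligibility check names new PrEP initiators, while the formal criteria and recruitment text admit continuing users; the rule should be reconciled and time on PrEP recorded

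*Protocol*

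**What the plan says.** PrEP status at entry is described in several places in the Protocol.

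- 7.2 (Study Population) refers to women "who are seeking PrEP at the Ward 21 Department of Health Clinic".
- 7.3.2 (Inclusion Criteria): "Taking PrEP at the Ward 21 clinic, as determined by clinic records".
- 7.3.3 (Exclusion Criteria): "Not on PrEP and/or not intending to use PrEP for the duration of the study".
- 8.1 (Recruitment): "Clinic personnel will identify AGYW seeking PrEP either at initiation or follow up".
- 8.3.2 (Screening and Enrollment Visit), in a bracketed list of example eligibility checks: "newly initiating PrEP at the clinic".
- The Schema, under study size: "Up to 110 women who accept PrEP will be consented and randomized". The SAP repeats this line and does not restate the PrEP criterion in more detail.

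No section sets a minimum or maximum time on PrEP. The Schema describes blocked randomization and states no stratification factor. The SAP's primary model for adherence has arm as its only predictor. Its sensitivity analysis for that endpoint names demographics, sexual behavior and HIV risk factors, but not time on PrEP. Under Protocol 10.1, the clinic record supplies age, HIV status and PrEP status at screening, and refill data for the three months of follow-up. A PrEP start date is not listed. Appendix 4 schedules no urine test at enrollment.

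**The concern.** A staff member working from the visit procedure in 8.3.2 could decline a continuing user whom 7.3.2 and 8.1 admit. The mix of new and continuing users would then depend on how the text is read.

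The mix matters for what the adherence result describes. Protocol 5.1 bases the need for the intervention on support within the first 1-3 months of use, and reports that adherence falls with time after initiation. The study cited in 11.3 for the control rate ("if we assume 40% PrEP adherence in the standard-ofcare arm") is described in 5.1 and 5.2 as a study of women initiating PrEP. If continuing users enroll, neither the rationale nor the planning rate clearly describes them. Without a start date in the data, the two groups may not be separable at analysis.

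**Working it through.** **Step 1. The wordings side by side.**

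| Source | Woman starting that day | Continuing user |
|---|---|---|
| 7.2, Schema | admitted | not ruled out |
| 7.3.2, 7.3.3 | admitted if the record shows her on PrEP | admitted |
| 8.1 | admitted | admitted |
| 8.3.2, read literally | admitted | not admitted |

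Sections 7.2, 7.3.2, 7.3.3 and 8.1 can be read together: the record of a woman dispensed PrEP that day can show her as taking it, and 8.3.2 allows a split visit. The conflict is 8.3.2 against 7.3.2 and 8.1, over continuing users.

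**Step 2. Does the mix affect the planned power?** The plan's figure is 80% power for 40% versus 60% (reading the 20% difference as points), alpha 0.05, 55 per arm. With the usual normal approximation, two-sided:

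power = Φ[(Δ√n − 1.96√(2p̄(1−p̄))) / √(p₁(1−p₁) + p₂(1−p₂))]

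= Φ[(0.20×7.416 − 1.96×0.7071) / 0.6928] = Φ(0.14) = 55.6%.

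The stated 80% is not reproduced (one-sided gives 67.8%). That shortfall does not come from the eligibility wording. Power for a 20-point gain at the other adherence rates quoted in Protocol 5.1:

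| Control rate | Power, 55 per arm |
|---|---|
| 25% | 59.7% |
| 27% | 58.6% |
| 40% | 55.6% |
| 48% | 56.7% |
| 62% | 65.0% |

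The whole range is about 9 points, and the planned rate is the lowest of the five.

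**Step 3. What would adjusting for user type gain?** Assume, for illustration, 62% adherence in new users and 27% in continuing users. These are the month 3 and month 9 values from one Johannesburg study in 5.1. Assume also that half of the participants are new users and that there is no arm effect.

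- Overall rate: 0.5×62 + 0.5×27 = 44.5%.
- Unadjusted SE of the arm difference: √(2×0.445×0.555/55) = 0.095, or 9.5 points.
- SD of the between-arm difference in the share of new users: √(2×0.25/55) = 0.095. Times 35 points, this is 3.3 points (95% range ±6.5).
- Share of the unadjusted variance: 0.25×0.35² / (0.445×0.555) = 0.0306/0.2470 = 12.4%.
- SE after removing it: 9.5×√(1 − 0.124) = 8.9 points, about 6% smaller.

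With a 20-point gap and the same overall rate, the chance-imbalance range is ±3.7 points, the variance share is 0.0100/0.2470 = 4.0%, and the SE falls by about 2%. These percentages do not depend on the number retained. They are on the risk-difference scale and serve as a guide to the relative-risk model.

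**The case against.** The strongest reply is that this is one stray phrase. It sits in a list of examples, in a part of the Protocol that 8.3 presents as additional detail on visits, while 7.3 is the formal criteria section and 7.1 admits women who meet all inclusion and no exclusion criteria. Much of this stands. A reader might infer three incompatible eligibility rules; the documents do not support that, because all the wordings except 8.3.2 can be reconciled. What remains is that no sentence gives 7.3 precedence, and the phrase sits in the step where eligibility is assessed.

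Four further inferences go too far.

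- *That 62% versus 27% measures new against continuing users.* Those are two time points in one study, measured in dried blood spots rather than urine. Protocol 5.2 shows that the measures differ: 48% of urine-positive women were at or above the blood-spot threshold. Continuing users here are still attending, and women not on PrEP are excluded, so they could adhere better than starters.
- *That a mix moves the control rate away from plan.* On the illustrative figures, a half-and-half mix gives 44.5%, nearer to 40% than the 62% for initiators alone.
- *That ±6.5 points is error on top of the usual uncertainty.* It is chance variation already inside the 9.5-point SE and reflected in the robust interval.
- *That the SRQ-20 model needs the same covariate.* Nothing in the documents links time on PrEP to the SRQ-20 outcome.

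**Conclusion.** The inconsistency is real and should be corrected. Section 8.3.2 conflicts with 7.3.2 and 8.1 on whether continuing users may enroll, and the documents do not say which governs. The consequence is an unclear target population for the adherence endpoint, because the rationale and the control-rate source describe initiators.

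The statistical effect is small. Both arms are drawn by randomization from the same pool, so the comparison is not biased. Adjustment would improve precision by about 6% if half are new users and the groups differ by 35 points, and by about 2% at 20 points. The split and the gap are assumptions, and the direction of any gap for the urine endpoint is unknown. The failure of the 80% power figure to reproduce is a separate issue, as is the difference between the 40% attributed to the cited study in 11.3 and the 25% reported for it in 5.1.

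**What to change.** 1. Reconcile 7.2, 7.3.2, 7.3.3, 8.1 and 8.3.2 to one statement of PrEP status at entry. Which group or groups to admit is the sponsor's choice.
2. If both groups stay eligible, add the PrEP start date to the items taken from the clinic record at screening (10.1), and define new versus continuing user before the data are unblinded.
3. In the SAP, pre-specify that indicator as a baseline covariate in the PrEP adherence model (Co-Primary Analysis 1). It need not be added to the SRQ-20 model.
4. Report the numbers of new and continuing users by arm, so that readers can see to whom the result applies.

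The cost is a protocol clarification, a short SAP edit and one extra variable from a record that staff already open. If the sponsor restricts entry to one group, accrual may fall below the planned 9-10 women per month.

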8.3.3. Week 2 Visit – Youth Friendship Bench SA participants only

- 1. Only participants randomized to the Youth Friendship Bench SA intervention will complete this visit, which will be their 2nd counseling session. This session may be conducted via phone.
- Schedule participant for their Week 4 visit in 14 days. The Week 4 visit will be scheduled as an in-person session for a time when they are able to return to the clinic.

8.3.4. Week 4 Visit

- 1. Confirm consent
- 2. Confirm locator information and update as needed
- 3. Collect psychosocial and behavioral data additional data (see Section 6).
- 4. Assess symptoms of common mental disorders
 - a. All participants will receive assessments per APC guidelines and referrals as needed. They will also complete the SRQ-20 with the lay counselor.
 - b. Participants Youth Friendship Bench SA arm will complete their 3rd counseling session.
- 5. Schedule participant's next visit
 - a. Standard-of-care participants will be scheduled for their Week 12 visit in 60 days.
 - b. Youth Friendship Bench SA participants will be scheduled for their Week 8 visit in 30 days. They will be offered the option to complete the Week 8 visit in-person or remotely (over the phone).
- 6. All participants will be asked to provide a urine sample for the tenofovir (TFV) point-of-care (POC) assay. Urine POC assay testing and drug-level feedback counseling based on assay results will be conducted by the lay Youth Friendship Bench SA for participants in both arms and proceed as described in Section 5.1.2. The urine assay results will be used for research purposes only and will not be included in the clinic record.
- 7. Schedule in-depth interviews for AGYW between the Week 4 and Week 12 study visit.

8.3.5. Week 8 Visit – Youth Friendship Bench SA participants only

- Participants randomized to the Youth Friendship Bench SA intervention will complete their 4th counseling session at this visit. This session may be conducted via phone
- 2. Schedule participant for their Week 12 visit in 30 days.
- Schedule participants for optional group session (either in person or via WhatsApp as they
 prefer, for between the Week 8 and 12 visits with the exact timing depending on availability of
 participants and enrollment accrual rates).

8.3.6. Week 12/Exit Visit

- 1. Collect psychosocial and behavioral data (see Section 6)
- 2. Assess symptoms of common mental disorders
 - a. All participants will receive assessments per APC guidelines and referrals as needed. They will also complete the SRQ-20 with the lay counselor.
 - b. Participants Youth Friendship Bench SA arm will complete their 5th counseling session.
- 3. All participants will be asked to provide a urine sample for the tenofovir (TFV) point-of-care (POC) assay. Urine POC assay testing and drug-level feedback counseling based on assay results will proceed as described in Section 5.1.2. The urine assay results will be used for research purposes only and will not be included in the clinic record.
- Complete termination procedures: exit participants, record any serious adverse events, ensure that participant is linked to and returns to the clinic for any routine services, and remove participants from any SMS communication as needed.

8.3.7. Interim Contacts and Visits

Interim contacts and visits (those between regularly scheduled follow up visits) may be performed at participant request or as deemed necessary by the clinic staff. We will ask participants about whether they attended the clinic for an interim visit at each study vist and will inquire about interim visit reason and outcome.

Some interim visits may occur for administrative reasons. For example, the participant may have questions for study staff. Other interim contacts and visits may occur in response to AEs experienced by study participants. When interim contacts or visits are completed in response to participant reports of AEs, study staff will assess the reported event clinically, record the event on the CRF, and provide or refer the participant to appropriate medical care.

8.3.8. Early Exit/Participant Withdrawal

Participants may voluntarily withdraw from the study for any reason at any time. The site investigator also may withdraw participants from the study to protect their safety and/or if they are unwilling or unable to comply with required study procedures. Participants also may be withdrawn if the study sponsors, government or regulatory authorities, or site IRBs terminate the study prior to its planned end date.

Every reasonable effort will be made to complete final evaluations for participants who terminate from the study prior to the last study assessment or visit; study staff will record the reason(s) for all withdrawals from the study in participants' study records. Participant non-adherence to the intervention(s) or PrEP is not a reason for participant withdrawal from the study and we will continue to follow participants even if they decline the interventions (e.g., reply "STOP" to the SMS messages) prior to the completion of follow-up.

8.4. Participant Retention and SMS Reminders for Intervention Arm

Participants will be in the study for 3 months of follow-up and retention procedures may include:

- Thorough explanation of the study visit schedule and procedural requirements during the informed consent process and re-emphasis at each study visit.
- Collection of detailed locator information at the Enrollment visit, and active review and updating of this information at each subsequent visit.
- Use of mapping techniques to establish the location of participant residences and other locator venues.
- Rapid and multi-faceted follow-up for missed visits (for participants in the Youth Friendship Bench SA arm only).
- Regular communication with the study community at large to increase awareness about HIV/AIDS and common mental disorders and explain the purpose of this research and the importance of completing research study visits.
- Use of appropriate and timely visit-reminder mechanisms via SMS (for participants in the Youth Friendship Bench SA arm only). Participants in the intervention arm will receive oneway SMS messages that remind them about their upcoming clinic visits and provide them with the appointment date and time.
- Use of the urine POC assay and corresponding drug-level feedback in both arms to support AGYW in returning to clinic for their PrEP refills and our accompanying mental health services and PrEP adherence assessment.

9.0 SAFETY MONITORING AND ADVERSE EVENT REPORTING

9.1. Management of health outcomes

5.1.1. Mental health symptoms

This section provides details on the management of symptoms of common mental disorders including self-harm, other psychiatric symptoms, and report of worsening symptoms throughout the study follow-up period.

Participants with a high SRQ-20 score at screening/enrollment visit: If the SRQ-20 score is greater than or equal to 7, the individual would be eligible for enrollment in this study but we will ensure that they have first completed standard-of-care procedures prior to study enrollment. As part of standard-of-care procedures, they will be offered a referral to talk with a social worker if they answered five or more questions on the SRQ-20 indicating that they have felt little pleasure in regular activities, have felt down or unhappy, and have experienced several items linked to common mental disorders (poor appetite, difficulty sleeping, etc.). The social worker will then meet with the young woman and make a further determination about referral for additional psychotherapy or pharmacotherapy as needed. AGYW who meet the SRQ-20 threshold for participation but require active management and care for untreated mental health symptoms, including psychiatric symptoms like hallucinations or severe somatic symptoms, will not be eligible for participation. However, they will be invited to return to the clinic and re-screen for eligibility in the study when their symptoms have stabilized (Figure 1).

Participants with a low SRQ-20 score at screening/enrollment: If the SRQ-20 score is less than 7, the individual would not be eligible for enrollment in this study but we will ensure that she is offered a referral to talk with a social worker as appropriate based on South African Department of Health Adult Primary Care Guidelines. Referrals will be provided to those who endorse at least one of the standard-of-care assessment items indicating that they have felt down or little pleasure in regular activities (**Appendix 1**) and five or more questions on the SRQ-20 indicating experience of somatic items linked to common mental disorders (poor appetite, difficulty sleeping, etc.; **Appendix 2**), regardless of SRQ-20 score. The social worker will then meet with the young woman and make a further determination about referral for additional

psychotherapy or pharmacotherapy as needed. We will also inform these AGYW that they can continue to receive PrEP at the study clinic.

Suicidal ideation, regardless of SRQ-20 score: The SRQ-20 includes one question on suicidal ideation ("Has the thought of ending your life been on your mind"), and anyone who endorses this item (regardless of their total SRQ-20 score) will be asked a series of three additional questions to determine suicidal intent ("Do you ever have thoughts of hurting or killing yourself?", "Are you currently thinking of killing yourself?", "Have you ever tried to kill yourself?"). They will also be provided referral to a social worker for further support as needed. Anyone who expresses suicidal intent or is deemed a risk to themselves or others will be ineligible for participation and immediately linked to inpatient care. They will only be able to re-screen into the study if and when their symptoms have stabilized and they not longer report self-harm or suicidal intent.

Worsening symptoms of common mental disorders throughout study follow-up: All participants will be asked whether their symptoms of common mental disorders have changed during the Week 4 and 12 visits and they will also complete the SRQ-20 at these time points. We will follow similar procedures as described for items a-c above, to ensure that individuals are linked with standard-of-care services regardless of SRQ-20 score. Those with symptoms of severe mental health distress or psychosis (e.g., unmanaged somatic symptoms, suicidal intent) will be linked to care and the study team will consider early termination from the study on a case-by-case basis.

